AVAL C	POSITIVE	MISSING	-99																													
AVAL C	MISSING	ANY	-99																													

CONFIDENTIAL

BMA117159

Column Header	Data Item	Codes	Derivation/Comments	Source data set
			
the same IMMU
 
(2) When IMMU changes from 0 to 1, impute IMMU=1 from the first record after the record known to be IMMU=0
 
(3) When IMMU changes from 1 to 0, impute IMMU = 1 until the record known to be IMMU=0
 
Only AVISIT and Day of collection is mentioned for these samples. Exact clock time information is missing. The workaround is to assign PREDOSE CYCLE 1 CTIME to SCREENING immunogenicity samples. For other cycles, as samples were collected at pre-dose, PREDOSE PK time is assigned. For EOT immunogenicity samples, CTIME will be same as PK time point. Use LOCF principle and do not include samples which were collected at non-PK time points except when it is positive. In this dataset, there were no confirmatory positive outcome, so LOCF principle will suffice.
	
IMM	Overall Immunogenicity Outcome 0=anti-GSK2857916 negative, 1=anti-	0 = negative	
 • If IMMU = 1 at any observation for a subject, IMM = 1 • else if all IMMU = -99, IMM = -99 	adis

CONFIDENTIAL

BMA117159

Column Header	Data Item	Codes	Derivation/Comments	Source data set
	GSK2857916 positive (at least one postdose)	1 = positive -99 = missing	Else IMM = 0 Fill in IMM in all rows for each subject	
ORDRESP	Best Confirmed Response	0,1,2,3,4,5,6	For PARAMCD=BCRSP, assign 0 for PD 1 for SD 2 for MR 3 for PR 4 for VGPR 5 for CR 6 for sCR Fill on all rows	adrs
BECOG	Baseline ECOG status	0 1 2	Fill on all rows	adqs
ECOG	ECOG status	0 1 2	Fill on all rows	
PRIORRX	Prior line of therapy		When addc.PARAMCD= LTXCPSCR, then PRIORRX = AVALC (Extract only the number and not the text) For AVALC = MORE THAN 10 LINES, PRIORRX=11 Fill on all rows	addc

CONFIDENTIAL

BMA117159

Column Header	Data Item	Codes	Derivation/Comments	Source data set
REFRAC	Refractory status	0 = Double 1 = Other	Fill on all rows	
MMTY	Type of Multiple Myeloma	0 = Secretary 1 = Non-secretory	When addc.MMYELOTY=SECRETORY, MMTY=0 When addc.MMYELOTY= NONSECRETORY, MMTY=1 If addc.MMYELOTY is missing, assign MMTY=-99 Fill on all rows.	addc
MMIGTY	Myeloma immunoglobulin	0 = IGA 1 = IGG 2 = IGM 3 = OTHER	When addc.PARAMCD=MYELOIG and AVALC=IGA, then MMIGTY =0 When addc.PARAMCD=MYELOIG and AVALC=IGG, then MMIGTY =1 When addc.PARAMCD=MYELOIG and AVALC=IGM, then MMIGTY =2 For AVALC which is not equal to IGA/ IGG /IGM, then MMIGTY=3 Fill on all rows	addc
BSTAGE	Stage at Screening	0 = I 1 = II 2 = III 3 = UNKNOW N or	When addc.PARAMCD = STAGESCR and AVALC = I, then BSTAGE = 0 When addc.PARAMCD = STAGESCR and AVALC = II, then BSTAGE = 1 When addc.PARAMCD = STAGESCR and AVALC = III, then BSTAGE = 2 When addc.PARAMCD = STAGESCR and AVALC = UNKNOWN or missing , then BSTAGE = 3 Fill on all rows	addc

CONFIDENTIAL

BMA117159

Column Header	Data Item	Codes	Derivation/Comments	Source data set
		missing		
MMLCTY	Myeloma Light Chain	0 = KAPPA LIGHT CHAIN 1 = LAMBDA LIGHT CHAIN	When addc.PARAMCD = MYELOLC and AVALC = KAPPA LIGHT CHAIN, then MMLCTY = 0 When addc.PARAMCD = MYELOLC and AVALC = LAMBDA LIGHT CHAIN, then MMLCTY = 1 Fill on all rows	addc

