2.3. Study Design

Overview of Study Design and Key Features	

Design Features
	
 • Part 1 Dose Escalation 
 ○ Population: Subjects with relapsed/refractory MM (originally planned to enrol up to 30 subjects. However, additional subjects were enrolled to explore a new intermediate dose group) ○ Objective: characterize safety, PK, PD, immunogenicity and establish RP2 dose of GSK2857916 ○ Two dosing schedules (Schedule 1 and Schedule 2) may be explored: 
 ▪ Schedule 1: GSK2587916 once every 3 weeks (21-day cycle) (n~20) ▪ Schedule 2: GSK2587916 once weekly for 3 consecutive weeks, 1-week rest (28-day cycle) (n~9). Schedule 2 was not actually explored. ○ Serial PK samples will be collected from all subjects in Part 1 • Part 2 Expansion Cohort(s) (n~50 subjects) 
 ○ Population: 
 ▪ Subjects with relapsed/refractory MM (up to 40 subjects) ▪ Subjects with lymphomas expressing BCMA (up to 10 subjects) ○ Objective: Further evaluate the safety, PK, immunogenicity, and clinical activity of GSK2857916 at the RP2 dose identified in Part 1 ○ MM and Lymphoma expansion cohorts will be analyzed separately ○ Sparse PK samples will be collected from all subjects • Genetics research samples will be collected predose from all subjects

Overview of Study Design and Key Features	
Dosing	
 • Part 1 Dose Escalation Initially, GSK2857916 will be administered (IV) via 60 min infusion once every three weeks (21 days = 1 cycle) on Schedule 1. Once an MTD1 or RP2D has been established on the once every 21-day (Schedule 1), the safety, tolerability, PK, and PD of once-weekly dosing (Schedule 2) of GSK2857916 may be explored as an additional cohort(s). • Part 2: Dose Expansion Phase Subjects enrolled in Part 2 dose expansion phase will be administered GSK2857916 at recommended phase 2 dose (RP2D) established based on Part 1 outcomes.
Time & Events	
 • Refer to Appendix 2: Schedule of Activities
Treatment Assignment	
 • This is a non-randomized open-label study.

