16. Sample(s) collected for analysis at central lab. The same sample will be used for BCMA (flow) and PD. On D8 only postdose PD assessment will be performed, if applicable (refer to footnote 18).
17. FISH testing at least for: t(4;14), t(14;16), 17p13del. FISH results from samples taken within 60 days prior to first dose are acceptable.
18. **Additional samples may be collected in some subjects (up to 6) for further exploration of PD.**
19. Archival tissue from up to 60 days prior to study is acceptable.
20. Collect sBCMA at C1D1 predose (within 30 minutes prior to SOI) and at EOI (± 5 minutes), C2D1 at predose (within 30 minutes prior to SOI) and at EOI (± 5 minutes).
21. Collect cytokines at predose (within 30 minutes prior to SOI) and EOI (± 5 min) (even when infusion is interrupted or halted) to assess allergic reaction
22. All ADA samples will be collected prior to each infusion
23. Flow cytometry performed central laboratory.
24. PK samples to be taken for both GSK2587916 and cys-mcMMAF measurement on C1D1, C2D1, C3D1, and C5D1 at predose (within 30 minutes prior to SOI) and at EOI (just before EOI).
25. Collect 1 PK sample at each subject's final visit.
26. Informed consent for optional genetics research should be obtained before collecting a sample.
27. Study drug administration ± 3 day window only.
28. Prophylaxis with prednisolone phosphate 1% or dexamethasone 0.1% 1 drop QID x 4 days starting 1 day prior to treatment
29. All participants should be followed for survival for 1 year from last subject last dose. and whether subsequent treatment for disease was given. Subject does not need to come in for visit. Participants who have completed treatment or the 3 month follow up visit (end of study) prior to amendment 5 will be reconsented for further follow up and survival status.
30. e-Diary to be completed at screening, then Days 1-7, 8, 15 of each treatment cycle. Upon implementation of the e-Diary, these assessments will be required.
31. OSDI and NEI-VFQ-25 to be administered during end of study treatment visit. Additional assessments for subjects who are experiencing corneal symptoms to be completed via telephone on a monthly basis for up to 1 year, or until resolution of symptoms (whichever comes first) during the follow-up period.
32. Exit interview to be performed within 21 days of end of study visit

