16.9. Appendix 9: Population Pharmacokinetic (PopPK) Analyses

16.9.1. Population Pharmacokinetic (PopPK) Dataset Specification

Any deviations between the dataset specification and the final dataset will be documented in the population pharmacokinetic analysis report.

General Description:

1. The type of variables should be either NUM or DATE/TIME unless specified otherwise
2. The dataset is sorted by ID, RTFDD, ANALYTE, ASCENDING EVID unless specified otherwise
3. The data items (columns) in the analysis-ready data file will be in the same order as described in the table below.
4. Exclude observations with DTYPE=IMPUTE
5. Include PKFL=Y (applicable to all datasets)
6. Same rules are applied for all baseline covariates. Baseline rules are as follows:
 - Use baseline value as defined by Stats in the lab test datasets and fill it on all rows for each subject;
 - If not defined by Stats, set to measurement nearest to, but prior to, time of first dose
 - Only in cases where Day 1 measurement is not available, but screening measurement is, the screening values will be used.
 - Only in cases where both the Day 1 measurement as well as screening measurement are unavailable, set to -99.
7. 3 significant figures for all values except C, STUDY, SUBJID, ID, CTIME, DATE, ANALN, BQL, MDV, MDV2, OCC, CYCLE, CMT, AGE, GENDER, CANCER, RACE, ETHN, CNC, EXTSMP
8. Only subjects with CANCER=0 will be included in this dataset as the data for the lymphoma patients will not be fully cleaned at the time of the database cut in 4Q2018.

CONFIDENTIAL

BMA117159

Column Header	Data Item	Codes	Derivation/Comments	Source data set
C	Line number/exclusion identifier	Row Number STM DRM PFD	Set to line/row number unless one or more of the following conditions are met, then set to code: 
 • STM = If a PK sample was taken but the date and/or time of the sample is missing and cannot be derived • DRM= PK samples for which dosing records are missing • PFD=PK samples with CONC reported as NA/NR/NQ/BQL/missing at pre-dose in CYCLE =1 	derived
STUDYID	Study ID		Unique identifier for a study	adpc
SITEID	Unique identifier for a study site			adsl
USUBJID	Unique subject identifier			adsl
SUBJID	Subject identifier from source data		SUBJID = SUBJID	adsl
ID	NONMEM subject identifier		Sequential subject identifier across studies after data is sorted by SUBJID. For study BMA117196, the ID will start with PPD For study 205678, the ID will start with PPD	derived

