AMT	Amount of GSK2857916 given (in mg)		AMT = ALTDOSE, where PARAMCD=ALTDOSE only on the dosing line. If infusion was stopped early and then restarted, the dosing information will be captured with more than one line. Each line will represent a part of the infusion (for example from start to first interruption and then from restart to end of infusion). AMT will have to be derived separately from restart of infusion until it is stopped. For all other lines use "0"	adex
INFD	Infusion Duration (day)		INFD is the infusion duration and is computed from start and stop time of infusion (in days) (AENDTM-ASTDTM)/60/60/24 This value will only be used on the dosing line. For all other lines use "0" If infusion was stopped early and then restarted, INFD will have to be derived separately from restart of infusion until it is stopped.	adex
INFH	Infusion Duration (h)		INFH is the infusion duration and is computed from start and stop time of infusion (in h) (AENDTM-ASTDTM)/60/60 This value will only be used on the dosing line. For all other lines use "0" If infusion was stopped early and then restarted, INFH will have to be derived separately from restart of infusion until it is stopped.	adex

CONFIDENTIAL

BMA117159

Column Header	Data Item	Codes	Derivation/Comments	Source data set
RATED	Rate of infusion (mg/day)		RATED = AMT/INFD; This value will only be used on the dosing line. For all other lines use "0" If infusion was stopped early and then restarted, RATED will have to be derived separately from restart of infusion until it is stopped.	derived
RATEH	Rate of infusion (mg/h)		RATEH = AMT/INFH This value will only be used on the dosing line. For all other lines use "0" If infusion was stopped early and then restarted, RATEH will have to be derived separately from restart of infusion until it is stopped.	derived
RTFDD	Relative time from start of first infusion on study (day)		$RTFDD = ((ADTM - ASTDTM) / 60 / 60 / 24)$	adpc, adex
RTFDH	Relative time from start of first infusion on study (h)		$RTFDH = ((ADTM - ASTDTM) / 60 / 60)$	adpc, adex
RTLDD	Relative time from start of the most recent infusion on study (h) done prior to the PK sample		For pre-dose samples, RTLDD will be calculated considering the most recent infusion done prior to the sample. For example, the RTLDD for the pre-dose in Cycle 2 will be computed from the start time of infusion in Cycle 1.	adpc

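### The PopPK rounding rule (SAP 16.9.1, item 7) does not exempt elapsed time, so on the day-scale column about 58% of end-of-infusion samples after Cycle 1 share the time of their infusion start

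*SAP*

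**What the plan says.** The general rules of SAP Section 16.9.1 fix the precision of the PopPK file: "3 significant figures for all values except C, STUDY, SUBJID, ID, CTIME, DATE, ANALN, BQL, MDV, MDV2, OCC, CYCLE, CMT, AGE". The list goes on with GENDER, CANCER, RACE, ETHN, CNC and EXTSMP and then closes. RTFDD and RTFDH are absent from it, as are RTLDD, RTLDH and the nominal-time columns.

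RTFDD is described as "Relative time from start of first infusion on study (day") and derived as "RTFDD = ((ADTM - ASTDTM) / 60 / 60 / 24"). RTFDH is the same quantity in hours. RTFDD also orders the file: "The dataset is sorted by ID, RTFDD, ANALYTE, ASCENDING EVID unless specified otherwise".

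Section 16.5.3 says the PopPK CSV file is created to this specification, so the rule governs stored values and not only a display.

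The infusion and cycle lengths are in Section 2.3: "GSK2857916 will be administered (IV) via 60 min infusion once every three weeks (21 days = 1 cycle"). The 16.9.1 derivation of nominal time likewise puts EOI at 1 h. Footnote 24 of Section 16.2.3.1 sets the Part 2 myeloma sampling: "C1D1, C2D1, C3D1, and C5D1 at predose (within 30 minutes prior to SOI) and at EOI (just before EOI"). Footnote 25 adds one sample at the final visit.

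**The concern.** After Cycle 1, elapsed time runs to tens of days, while the event to be resolved, infusion start to EOI, lasts one hour. Three significant figures cannot hold both. If the stored time of an EOI sample equals the stored time of the dosing record, no drug from that infusion has yet entered the body as far as the model is concerned. The prediction is then the trough, while the observation is close to the peak.

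Expansion-cohort PopPK parameters and covariate effects are a secondary endpoint (Section 2.2). Part 2 myeloma subjects contribute pre-dose and EOI samples at four cycles plus one final sample, so three of their four EOI samples (C2, C3, C5) are exposed. The PopPK output feeds CMAX, CTAU, AUC and the time-average AUC variables used in the corneal-event and efficacy exposure-response analyses (Section 16.10.1).

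**Working it through.** The SAP gives no figure for time resolution, so there is none to reproduce. The check rounds the start and EOI times and counts ties.

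**Inputs**
- Infusion length 1 h = 1/24 = 0.0417 day (Section 2.3).
- 21-day cycle, so C2, C3 and C5 start nominally on days 21, 42 and 84, or at 504, 1008 and 2016 h.
- Dosing window of ±3 days (Section 16.2.3.1, footnote 27).

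**Day column, RTFDD**
- Rounding step: 0.1 day = 2.4 h from day 10 to day 100; 1 day from day 100.
- Nominal schedule: 21 and 21.042 both become 21.0; 42 and 42.042 become 42.0; 84 and 84.042 become 84.0. Every later EOI sample ties.
- Varying start times (assumed evenly spread over the rounding grid): P(tie) = 1 − gap/step = 1 − 0.0417/0.1 = 58.3%. Simulation gave 58–59%, with starts spread evenly over ±3 days or shifted by whole days with clock-time SD of 1 or 2 h.
- The other 42% or so move up one step, to 2.4 h after the start instead of 1 h.
- From day 100: 1 − 0.0417/1 = 95.8%. This applies only where C5 slips at least 16 days beyond its nominal day 84.

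The tie rate on days 10–100 depends on the true gap between start and sample:

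| Gap (h) | 1 − gap/2.4 |
|---|---|
| 0.5 | 79% |
| 0.95 (drawn 3 min early) | 60% |
| 1.0 | 58% |
| 1.25 | 48% |
| 2.0 | 17% |

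Ties are therefore the majority only for gaps below 1.2 h.

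**Hour column, RTFDH**
- C2: the step is 1 h; 504 and 505 stay apart, so 0% tie.
- From 1000 h the step is 10 h: 1 − 1/10 = 90%.
- C3: the ±3-day window spans 936–1080 h, so about 80/144 = 56% of starts are past 1000 h, and 0.56 × 0.90 ≈ 50% (simulated 50–55%, including samples drawn 3 min early, the higher figures being mostly those).
- C5: simulated 88–90%.

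**What survives rounding**
- Cycle 1 EOI: 1.00 h or 0.0417 day, unaffected.
- RTLDH (hours since the latest infusion): 1.00 h, unaffected.
- DATE is exempt and CLOCK is stored in hour-and-minute format, so event times remain in the file.

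**Does the exempt name CTIME cover elapsed time?** No column has that name. In the list it stands before DATE and ANALN, where the table has CLOCK, DATE and ANALYTE, and the IMMU row uses CTIME for clock time. Read that way, RTFDD and RTFDH are still rounded.

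**After a change.** With 4 significant figures no simulated EOI sample ties, and the largest error between day 10 and day 100 is about 7 min. With 5 figures it is under 1 min. Four decimal places give a step of 0.0001 × 86,400 = 8.6 seconds throughout.

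**The case against.** The strongest reply is that nothing in the SAP makes RTFDD the model's time variable. It is stated only as a sort key. DATE, CLOCK and RTLDH keep the one-hour gap, so an analyst could rebuild exact times. This stands, and it makes the modelling consequence conditional. Clearance in L/day (Section 16.10.1) points to a day scale but does not settle the column.

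Second, the exemption list is plainly out of date: STUDY, CTIME, ANALN, GENDER and RACE are not the table's headers, and a literal reading would round identifiers too. Someone building the file might sensibly not apply it literally. That is a reason to correct the list, since the text as it stands instructs the rounding.

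Third, the misfit might be noticed. Section 16.9.2 plans exploratory analysis, goodness-of-fit plots and residual inspection, and 16.9.1 allows documented departures from the specification. These may catch the error, but they do not correct the rule.

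Three stronger readings are tempting, and the documents do not support them:
- **The model will match peaks to troughs.** This needs RTFDD as model time, which is not stated. The sort order does not add to the fault either: with exact times the dosing line also precedes its EOI sample.
- **Clearance would be biased by a known factor.** Illustrative pooled fits with assumed PK values gave rounded-to-exact clearance ratios of about 0.4–0.5 using Part 2 alone and 0.58–0.65 with Part 1 subjects added. Section 9 plans to pool both parts, Part 1 has dense Cycle 1 sampling that rounding hardly touches, and neither fit is the planned mixed-effects model.
- **Every exposure metric is affected.** Cumulative dose, AMT, IDOSE and TOTCYC come from dosing records, not from PopPK output.

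**Conclusion.** The rule as written stores wrong elapsed times. On RTFDD about 58% of EOI samples at C2, C3 and C5 tie with their infusion start, and the rest are placed about 2.4 h after it. This assumes a 60-minute gap and start times spread over the rounding grid; on the exact nominal schedule all of them tie, and from day 100 about 96% would. On RTFDH the fault is uneven (about 0%, half and 90% at C2, C3 and C5), so a majority claim holds for the day column only.

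If the model reads RTFDD, peak samples would be given pre-infusion predictions. The PopPK parameters, CMAX, CTAU, AUC and the time-average AUC variables would then be biased by an amount the documents do not establish. The specification should be corrected before the file is used.

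**What to change.** In Section 16.9.1:
- Exempt RTFDD, RTFDH, RTLDD, RTLDH, the nominal-time columns and the infusion columns (AMT, INFD, INFH, RATED, RATEH) from item 7. Alternatively, carry RTFDD to at least 4 decimal places, or at least 5 significant figures. Decimal places are the safer choice, because 5 figures still means a 14.4-minute step (0.01 day) from day 100.
- Make the exemption names match the headers: CTIME to CLOCK, ANALN to ANALYTE, STUDY to STUDYID, GENDER to SEX, RACE to RACEN. Add the identifiers SITEID and USUBJID.
- State which column is the model time.

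The cost is a few lines of specification and, if the file already exists, one rerun of the dataset program. No new data are needed.

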2. SUMMARY OF KEY PROTOCOL INFORMATION

There are no changes to the planned analyses, analysis method and data handling convention as described in [RAP amendment 1](#). The only update is the list of displays for end of study analysis.

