2.2. Study Objective(s) and Endpoint(s)

Objectives	Endpoints
Primary Objectives	Primary Endpoints

 To determine safety, tolerability, maximum tolerated dose (MTD), and recommended phase (RP2) dose and schedule of GSK2857916 administered 	
 Adverse events (AE) and changes in clinical signs and laboratory parameters
Secondary Objectives	Secondary Endpoints

 To evaluate the pharmacokinetic (PK) profile of GSK2857916 and the breakdown product cys-mcMMAF after intravenous (IV) single and repeat dose administration in subjects with relapsed/refractory MM and BCMA expressing lymphomas 	
 GSK2857916 and cys-mcMMAF PK parameters following IV single and repeat dose administration during dose escalation as data permit (e.g., AUCs C_{max}, t_{max}, CL, V_{ss}, t_{1/2} [single dose], C_{max} and C_{trough} [repeat dose]). GSK2857916 population PK parameters in expansion cohorts at the RP2 dose (e.g. clearance (CL), volume of distribution (V_d)), and relevant covariates which may influence exposure (e.g. age, weight, or disease-related covariates e.g. BCMA expression)

 To assess anti-drug antibody (ADA) formation after IV single and repeat dose administration of GSK2857916 	
 ADA incidence and titers after single and repeat IV dosing of GSK2857916

 To explore the initial anti-tumor activity of GSK2857916 in subjects with relapsed/refractory MM and BCMA expressing lymphomas 	
 Clinical activity measured as Overall Response Rate (ORR) which is defined as follows: 
 For MM: the percentage of subjects achieving confirmed partial response or better (≥PR) In addition, the percentage of subjects with minimal response (MR) will be assessed for clinical benefit rate (CBR) (Appendix 1 of protocol) For Lymphomas: the percentage of subjects achieving PR or better (≥PR) (Appendix 2 of protocol)
Exploratory Objectives	Exploratory Endpoints

 To evaluate PD markers in MM after treatment with GSK2857916 	
 sBCMA levels, BCMA receptor occupancy and cell death markers in subjects with MM.

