9. PHARMACOKINETIC ANALYSES

The pharmacokinetic (PK) analyses will be based on the Pharmacokinetic population, unless otherwise specified.

Pharmacokinetic data from Part 1 of the study will be analyzed using standard non-compartmental methods, and combined data from Part 1 and Part 2 of the study will be analyzed in a population approach using nonlinear mixed effects modeling. Full details are presented in [Appendix 12](#): List of Data Displays.

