10. POPULATION PHARMACOKINETIC (POPPK) ANALYSES

The primary goal of this analysis is to characterize the population pharmacokinetics of GSK2857916 and associated analytes after intravenous of GSK2857916 in participants with multiple myeloma, data permitting. The influence of subject demographics, baseline characteristics including disease activity, and other covariates on the pharmacokinetics of GSK2857916 will be investigated. The individual subject pharmacokinetic parameters will be estimated and documented for the purposes of any subsequent exposure-response (PK/PD) analyses. This analysis will be performed by CPMS and reported separately.

A summary of the planned population pharmacokinetic analyses is outlined below:

- Plasma concentration-time data for GSK2857916 ADC will be subjected to nonlinear mixed effects modelling using the program NONMEM to develop a population pharmacokinetic model. A similar approach may be used on the data from two analytes (ADC and cys-mcMMAF) and three analytes (ADC, total antibody, and cys-mcMMAF) together.
- Individual *post hoc* estimated pharmacokinetic parameters will be summarized descriptively.
- To support this analysis, a population PK dataset will be generated. The details for the dataset specifications are provided in [Appendix 9: Population Pharmacokinetic \(PopPK\) Analyses](#).

Detailed population PK methodology is presented in [Appendix 9: Population Pharmacokinetic \(PopPK\) Analyses](#).

**11. PHARMACODYNAMIC (AND / OR BIOMARKER)
ANALYSES**

The pharmacodynamic analyses will be documented in a separate RAP.

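### No population PK parameter is planned for the lymphoma cohort, although the secondary PK endpoint covers both expansion cohorts

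*SAP*

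**What the plan says.** **Endpoint and design (RAP Amendment 1).** Section 2.2 sets a secondary objective on the PK profile after single and repeat "dose administration in subjects with relapsed/refractory MM and BCMA expressing lymphomas". One of its endpoints is "GSK2857916 population PK parameters in expansion cohorts at the RP2 dose", with clearance and volume as examples, plus covariates that may influence exposure. Section 2.3 makes lymphoma one of the two expansion cohorts, with up to 10 of about 50 subjects, and states: "Sparse PK samples will be collected from all subjects".

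**Analysis scope (RAP Amendment 1).** Section 9 says that "combined data from Part 1 and Part 2 of the study will be analyzed in a population approach using nonlinear mixed effects modeling" and excludes no tumour type. Section 10 gives the goal as characterising population PK "in participants with multiple myeloma, data permitting", and Section 16.9.2 repeats the myeloma scope. Item 8 of Section 16.9.1 fixes it in the dataset: "Only subjects with CANCER=0 will be included in this dataset as the data for the lymphoma patients will not be fully cleaned" at the 4Q2018 cut. CANCER=0 is myeloma and CANCER=1 is lymphoma.

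**End-of-study RAP.** Section 2 states: "There are no changes to the planned analyses, analysis method and data handling convention". Only the display list is updated. For lymphoma PK it keeps concentration tables, plots and listings, together with QTc-against-concentration displays.

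**The concern.** Sections 2.2 and 9 point to both diseases, while Sections 10 and 16.9 point to myeloma alone. The restriction was sensible for the 4Q2018 cut, because Section 3.3 foresaw a myeloma analysis before the lymphoma cohort finished. The stated reason lapses once lymphoma data are clean, and the end-of-study RAP is the natural place to lift the rule. It does not.

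At stake is a secondary PK question that the trial set itself. Lymphoma subjects give sparse samples, a design that depends on a population model for clearance and volume. Leaving them out of that model leaves the question without an estimate in their cohort, and no document says that this was intended.

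**Working it through.** The plan gives no figure to reproduce on this point. The check sets its sections side by side and then counts displays and samples.

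**1. Is the restriction declared?** Table 1 in Section 2.1 of RAP Amendment 1 records several PK changes: the PK population definition, the repeat-dose cys-mcMMAF Cmax, the urine collection interval and the added analyte ratios. It has no row saying that the population PK endpoint now covers one disease.

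**2. Does another specified route give clearance or volume in lymphoma?** Section 9.1.2.1 derives the Table 7 parameters from Cycle 1 data in Part 1. Section 4 says that Part 1 is exclusively myeloma. So Table 7 supplies nothing for lymphoma. The accumulation and analyte ratios in Sections 9.3.1.2 and 9.3.1.3 have their own definitions from end-of-infusion and trough concentrations, but they are not clearance or volume.

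**3. Which lymphoma parameter displays exist?**

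| Display type, lymphoma | RAP Amendment 1 | End-of-study list |
|---|---|---|
| Derived-parameter summaries | 4 (4.0053, 4.0063, 4.0073, 4.0083) | 0 |
| Derived-parameter listings | 4 (4.0091, 4.0101, 4.0111, 4.0121) | 0 |
| Accumulation-ratio tables | 4 (4.0163, 4.0173, 4.0183, 4.0193) | 0 |
| Analyte-ratio tables | 3 (4.0203, 4.0213, 4.0223) | 0 |
| Accumulation-ratio listings | 4 (1.0711, 1.0721, 1.0731, 1.0741) | 0 |

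The end-of-study list keeps 3 concentration tables, 9 concentration figures and 3 concentration listings for lymphoma. Its Section 1.1 explains that lymphoma output will be mostly listings because the cohort is small. That does not explain why the parameter listings are dropped too.

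**4. How much data is involved?** Footnotes 18 and 19 of Section 16.2.3.3 schedule 4 samples at C1D1, 2 each at C2D1, C3D1 and C5D1, and 1 at the final visit.

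- Per subject: 4 + 2 + 2 + 2 + 1 = 11
- Ceiling per analyte: 11 × 10 = 110
- Without the Cycle 1 pre-dose sample, which Section 16.9.1 codes for exclusion when not quantifiable: 10 × 10 = 100
- Share of the expansion phase: 10 / 50 = 20%

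Both totals assume that 10 subjects enrol and all reach Cycle 5.

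**The case against.** The strongest reply is that the myeloma scope is open and reasoned. Sections 10 and 16.9.2 state it, Section 16.9.1 explains it, and Section 2.3 says that the two expansion cohorts are analysed apart. Population PK goes into a separate report, and Section 16.9.1 lets that report document departures from the dataset specification. The contents list of RAP Amendment 1 shows no population PK display section, so absence from the end-of-study display list proves little on its own.

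Much of this stands. The display list alone would be weak evidence. But the rule sits in the dataset specification, and the end-of-study RAP says that data handling is unchanged. Separate reporting and the clause on departures permit lymphoma to be added; they do not plan it. Analysing the cohorts apart is no reason to leave one unanalysed.

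A reader might also infer three stronger points that the documents do not support:

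- **That no PK parameter of any kind is planned for lymphoma.** RAP Amendment 1 lists the displays in the table above. The gap concerns population PK parameters.
- **That a planned test of disease type on clearance is defeated.** Section 16.9.2 names disease status as a covariate without defining it as tumour type, and Section 2.2 gives BCMA expression as its disease-related example. A constant CANCER column is harmless in itself.
- **That 110 concentrations per analyte are lost.** That is a ceiling, and the lymphoma concentrations are still summarised, plotted and listed.

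**Conclusion.** The concern holds for population PK. Sections 2.2 and 9 conflict with Sections 10 and 16.9. The restriction rests on a reason specific to one database cut, is not declared as a change, and is carried into the end-of-study plan. Followed as written, the plan leaves a secondary endpoint unestimated in one of two expansion cohorts: up to 10 of about 50 subjects, each with at most 11 scheduled samples per analyte.

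The lymphoma displays in RAP Amendment 1 do not close the gap. Its derived-parameter displays have no Table 7 derivation outside Part 1, its ratios do not give clearance or volume, and none of these displays is in the end-of-study list.

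This assumes that the separate population PK report follows the specification shown here; that report is not available. The point should be fixed, but it concerns a secondary endpoint in an uncontrolled Phase I trial and does not touch the safety objective or the myeloma results.

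**What to change.** 1. In Section 16.9.1, state that the CANCER=0 rule applies to the 4Q2018 cut only.
2. In the end-of-study RAP, add the lymphoma subjects (CANCER=1) to a population PK update. Obtain their individual post hoc clearance, volume and Cycle 1 exposure from the final myeloma model, and summarise them separately from myeloma, in line with Section 2.3.
3. State whether the lymphoma derived-parameter displays of RAP Amendment 1 are kept. If they are, say how the parameters are derived from Part 2 data.
4. If the sponsor prefers a myeloma-only endpoint, record that in Table 1 with the reason.

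The cost is one extra modelling run on samples already scheduled. With at most 10 sparsely sampled subjects the estimates will be imprecise, so the plan should describe them and not promise a formal test of disease type as a covariate.
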